5.4. Handling Missing Data

Missing data for primary [REDACTED] effectiveness endpoints will not be imputed. The IDEEL-SB score is calculated if at least 50% (10 items) of the 20 items within the dimension are completed (non-missing), otherwise the score is set to missing.

5.5. Multiplicity Strategy

No multiplicity adjustment needs to be considered for the effectiveness endpoints since no formal hypothesis testing will be conducted.

5.6. Subgroup Analysis and Effect of Baseline Factors

No subgroup analyses are currently planned.

5.7. Interim Analysis for Efficacy

No interim analyses for effectiveness endpoints are currently planned.

6. Safety Analysis Strategy

The focus of the safety analysis will be a comprehensive descriptive assessment of occurrence of AE as well as the other listed parameters. Therefore, no inferential testing will be done for the safety analysis.

6.1. Safety Endpoints

The safety endpoints for this study are:

- Biomicroscopy findings (including corneal staining)
- BCVA
- AEs
- Device deficiencies

6.2. Safety Hypotheses

No inferences are to be made on the safety endpoints; therefore, no hypotheses are formulated.

6.3. Statistical Methods for Safety Analyses

The FAS will be used for all safety analyses. All safety endpoints will be summarized descriptively overall and by group.

6.3.1. Adverse Events

The applicable definition of an AE is in the study protocol. All AEs will be collected from the time of signed IC until study participation is complete. AEs will be coded using the most current available version of the Medical Dictionary for Regulatory Activities (MedDRA) at the time of the data-cut.

All analyses described will be based on treatment-emergent adverse events (TEAEs), if not otherwise specified. TEAEs are those events with onset dates occurring on or after the first dose of study treatment until the end of the study. AEs with an onset date missing will be considered as TEAE.

- **AEs related with study device:** AEs recorded on the AE eCRF page, Relationship to Study Device = Related) and those of unknown relationship (i.e., no answer to the question “Relationship to Study Device”).
- **AEs related with test procedure:** AEs recorded on the AE eCRF page, Relationship to Test Procedure = Related) and those of unknown relationship (i.e., no answer to the question “Relationship to Test Procedure”).
- **Serious adverse events (SAEs):** AEs recorded on the AE eCRF page, Was this a Serious Adverse Event? = Yes.

- **AEs resulting in study device permanent discontinuation:** AEs recorded on the AE eCRF page, Action Taken Due To Adverse Event = Study Device Permanently Discontinued.
- **AEs resulting in death:** AEs recorded on the AE eCRF page, Death = Yes or Outcome = Fatal.
- **Ocular AEs:** AEs recorded on the AE eCRF page, Eye = OD or OS.

TEAEs will be summarized as the number and percentage of subjects/eyes by MedDRA Preferred Terms (PT) as an event category. Each subject/eye will be counted only once within a given PT. TEAEs will be displayed in terms of frequency tables sorted on decreasing frequency of PT. In case of equal frequency regarding PT, alphabetical order will be used. In case any specific TEAE does not have MedDRA PT coded terms, it will be summarized under the “Uncoded” category.

The following tables will be created for non-ocular TEAEs (subject-level summary):

- The overall summary table of non-ocular TEAEs will include the number of non-ocular TEAEs and the frequency (number and percentage), and the corresponding 95% CI of subjects with:
 - Any non-ocular TEAE
 - Any moderate non-ocular TEAE
 - Any severe non-ocular TEAE
 - Any non-ocular TEAE related with study device
 - Any non-ocular TEAE related with test procedure
 - Any serious non-ocular TEAE
 - Any serious non-ocular TEAE related with study device
 - Any serious non-ocular TEAE related with test procedure
 - Any non-ocular TEAE resulting in study device permanent discontinuation
 - Any non-ocular TEAE resulting in death
- Non-ocular TEAEs by PT
- Serious non-ocular TEAEs by PT
- Non-ocular TEAEs related with study device by PT

For ocular TEAEs, the following data will be summarized (eye-level summary):

- The overall summary table of ocular TEAEs will include the number of ocular TEAEs and the frequency (number and percentage), and the corresponding 95% CI of eyes with:
 - Any ocular TEAE
 - Any moderate ocular TEAE
 - Any severe ocular TEAE
 - Any ocular TEAE related with study device
 - Any ocular TEAE related with test procedure
 - Any serious ocular TEAE
 - Any serious ocular TEAE related with study device
 - Any serious ocular TEAE related with test procedure
 - Any ocular TEAE resulting in study device permanent discontinuation
 - Any ocular TEAE resulting in death
- Ocular TEAEs by PT
- Serious ocular TEAEs by PT
- Ocular TEAEs related with study device by PT

Supportive listings will be provided for all TEAEs. Ocular TEAEs will be flagged.

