2.1. Full Analysis Set (FAS)

The FAS will include all subjects/eyes exposed to at least one dose of Systane Ultra PF. The FAS will serve as the primary analysis set for all effectiveness and safety analyses.

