3.1. General Methods

In general, summaries will present data overall and by the following groups:

- Group 1: subjects with mild to moderate DE receiving Systane Ultra PF.
- Group 2: subjects with end of day CL-related dryness receiving Systane Ultra PF.

No hypothesis testing will be performed. Whenever applicable, 95% confidence intervals (CIs) will be provided. For proportions, 95% CIs will be calculated using the exact Binomial (Clopper-Pearson) method [1]. 95% CIs of a normal distribution for means will be provided, as needed.

All relevant subject data will be included in listings. The listings will be sorted by subject ID, and other characteristics (age, sex, eye(s), etc.), if necessary.

Data collected for IDEEL-SB, CLDEQ-8, [REDACTED], BCVA, [REDACTED] and Biomicroscopy findings at unscheduled visits may be included in by-visit summaries and analyzed in the same fashion as the data collected at scheduled visits except where otherwise noted.

SAS® version 9.4 or higher will be used for all statistical analyses and tabulations.

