6.3.2. BCVA

BCVA will be assessed per standard practice at the Screening/Baseline visit (Day 1) and at Visit 3 (and at unscheduled and early exit visits, as necessary).

For each eye, the distance visual acuity (VA) will be collected as per the site's standard of care practice using charts validated for the specific testing distance, which may include for example, 6 m for Snellen chart, 20 ft for Snellen chart, decimal chart and logMAR score. The values for BCVA will be presented in logMAR. BCVA will be summarized as a continuous variable at each analysis visit (Baseline and Visit 3) [eye-level summary]. The mean BCVA score will be presented together with the corresponding 95% CI. In addition, the change from Baseline will be summarized at Visit 3.

A supportive listing for BCVA assessments will be provided.

Derivations:

- BCVA (logMAR) = $-\log_{10} (20 / \text{Snellen VA 20 ft fractions})$ if measured in 20 ft for Snellen chart.
- BCVA (logMAR) = $-\log_{10} (6 / \text{Snellen VA 6 m fractions})$ if measured in 6 m for Snellen chart.
- BCVA (logMAR) = $-\log_{10} (\text{decimal acuity})$ if measured in decimal chart.

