Table 14.1.3.1.1: Summary of Demographics and Baseline Clinical Characteristics – FAS

Table 14.1.3.1.2: Summary of Demographics and Baseline Clinical Characteristics by Site – FAS

Table 14.1.4.1: Summary of Treatment Duration and Missed Doses – FAS

Table 14.2.1.1.1.1: Summary of IDEEL-SB Score by Analysis Visit (Group 1) – FAS

Table 14.2.1.1.1.2: Summary of IDEEL-SB Score by Analysis Visit (Group 1) – PP

Table 14.2.1.2.1.1: Summary of CLDEQ-8 Score by Analysis Visit (Group 2) – FAS

Table 14.2.1.2.1.2: Summary of CLDEQ-8 Score by Analysis Visit (Group 2) – PP

Table 14.3.1.1: Overall Summary of Non-Ocular Treatment-Emergent Adverse Events (TEAEs) - FAS

Table 14.3.1.2.1: Summary of Non-Ocular Treatment-Emergent Adverse Events (TEAEs) by MedDRA PT – FAS

Table 14.3.1.2.2: Summary of Serious Non-Ocular Treatment-Emergent Adverse Events (TEAEs) by MedDRA PT – FAS

Table 14.3.1.2.3: Summary of Non-Ocular Treatment-Emergent Adverse Events (TEAEs) Related with Study Device by MedDRA PT – FAS

Table 14.3.1.3: Overall Summary of Ocular Treatment-Emergent Adverse Events (TEAEs) - FAS

Table 14.3.1.4.1: Summary of Ocular Treatment-Emergent Adverse Events (TEAEs) by MedDRA PT – FAS

Table 14.3.1.4.2: Summary of Serious Ocular Treatment-Emergent Adverse Events (TEAEs) by MedDRA PT – FAS

Table 14.3.1.4.3: Summary of Ocular Treatment-Emergent Adverse Events (TEAEs) Related with Study Device by MedDRA PT – FAS

Table 14.3.2.1: Summary of BCVA Score (logMAR) by Analysis Visit – FAS

Table 14.3.3.1: Summary of Biomicroscopy Findings by Analysis Visit – FAS

Table 14.3.3.2: Shift from Baseline to Visit 3 Biomicroscopy Findings – FAS

Table 14.3.3.3: Summary of Corneal Staining by Analysis Visit – FAS

Table 14.3.3.4: Shift from Baseline to Visit 3 Corneal Staining – FAS

Table 14.3.3.5: Summary of Corneal Infiltrates by Analysis Visit (Group 2) – FAS

Table 14.3.4.1: Summary of Device Deficiencies - FAS

Listing 16.2.1.1: Listing of Subject Disposition

Listing 16.2.1.2: Listing of Missed Visits – FAS

Listing 16.2.2.1: Listing of Protocol Deviations – FAS

Listing 16.2.3.1: Listing of Demographics and Baseline Clinical Characteristics – FAS

Listing 16.2.3.2: Listing of Medical History and Concomitant Medication – FAS

Listing 16.2.3.3: Listing of Missed Doses - FAS

Listing 16.2.4.1: Listing of IDEEL-SB Questionnaire (Group 1) – FAS

■■■■■
Listing 16.2.4.3: Listing of CLDEQ-8 Questionnaire (Group 2) – FAS

■■■■■

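### Eye-level 95% CIs for ocular TEAEs and mean BCVA ignore the correlation between a subject's two eyes, and no listed table counts subjects with any TEAE or any ocular TEAE

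*SAP*

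**What the plan says.** SAP 6.3.1 splits TEAEs by unit of analysis. For non-ocular events it states: "The following tables will be created for non-ocular TEAEs (subject-level summary"). For ocular events the unit becomes the eye, and the overall summary shows the number, percentage "and the corresponding 95% CI of eyes with" each of ten categories of event. In SAP 6.3.2 BCVA is also an eye-level summary at Baseline and Visit 3, and "The mean BCVA score will be presented together with the corresponding 95% CI".

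The interval methods are in SAP 3.1: "For proportions, 95% CIs will be calculated using the exact Binomial (Clopper-Pearson) method", and normal-theory intervals for means. SAP 6.3 adds that "All safety endpoints will be summarized descriptively overall and by group". The analysis set is wide: "The FAS will include all subjects/eyes exposed to at least one dose of Systane Ultra PF".

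The output list in SAP section 13 has one overall table for non-ocular TEAEs (14.3.1.1) and one for ocular TEAEs ("Table 14.3.1.3: Overall Summary of Ocular Treatment-Emergent Adverse Events (TEAEs) - FAS"). No title covers all TEAEs together. SAP 6.2 says "No inferences are to be made on the safety endpoints".

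Precision was planned in Protocol 6.4.1 and SAP section 8 for an AE proportion of 0.0543 in a sample of 54, with a half-width of 0.060.

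**The concern.** Clopper-Pearson and the ordinary interval for a mean both treat every observation as independent. Two eyes of one person, given the same drops by the same hand, are unlikely to be independent. Neither document mentions a study eye, a clustered variance, a mixed model or resampling by subject. With positive correlation, 108 eyes carry less information than 108 independent units, and an interval computed as if they were independent is too short.

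The second part concerns what is counted. The planning figure is for 54 subjects, but the ocular tables count eyes and the subject tables leave ocular events out. For an eye drop, a reader will first ask how many subjects had an ocular event, and no listed table says. The eye percentage cannot stand in for it, because the same percentage of eyes fits a range of subject rates.

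The non-ocular TEAE intervals are unaffected, being by subject. So is biomicroscopy, for which no CI is specified.

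**Working it through.** **Inputs.** From the documents: 54 evaluable subjects (27 per group), 68 recruited, AE proportion 0.0543, half-width 0.060, two-sided 95%. Assumed: the between-eye correlation ρ, shown over a range; the same event rate p in both eyes; both eyes of every subject counted; and 0.0543 as a scenario for the eye rate (the documents label it only as AEs).

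**The plan's own figure.** The half-width is 1.96 × √(0.0543 × 0.9457 / 54) = 0.0604, which matches 0.060. All eight cells of the precision table also reproduce. The planning unit is therefore the subject. The same formula with 108 independent eyes gives 0.043.

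**Loss of information.** Two eyes per subject give a design effect of 1 + ρ. The effective number of eyes, 108/(1 + ρ), is 72, 60 and 54 at ρ = 0.5, 0.8 and 1.

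**Coverage of the ocular TEAE interval.** For one subject, P(both eyes affected) = p² + ρp(1 − p) and P(exactly one) = 2(1 − ρ)p(1 − p). Convolving over N subjects gives the exact distribution of affected eyes. Coverage is the probability that the Clopper-Pearson interval on 2N eyes contains p.

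| Subjects | True eye rate | ρ = 0 | 0.25 | 0.5 | 0.8 | 1 |
|---|---|---|---|---|---|---|
| 54 (pooled) | 5.43% | 96.8% | 94.5% | 91.8% | 89.0% | 87.9% |
| 27 (one group) | 5.43% | 99.2% | 98.3% | 97.4% | 96.2% | 94.4% |
| 27 (one group) | 10% | 96.0% | 93.3% | 90.3% | 87.5% | 89.5% |
| 68 (pooled, maximum) | 5.43% | 96.4% | 93.9% | 91.1% | 87.4% | 81.4% |
| 34 (one group, maximum) | 5.43% | 96.6% | 94.2% | 91.0% | 85.5% | 81.5% |
| 34 (one group, maximum) | 10% | 97.7% | 95.9% | 93.7% | 91.3% | 92.4% |

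The last three rows apply if all 68 recruited subjects are treated and so enter the FAS; 34 per group assumes an equal split. In the first row, the upper limit falls below the true rate in 4.5%, 5.9% and 4.9% of trials at ρ = 0.5, 0.8 and 1, against a nominal maximum of 2.5%. With 27 subjects at 5.43% there are no such misses, because even 0/54 eyes gives an upper limit of 6.6%.

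**Example.** Six affected eyes of 108 give a planned interval of 2.1% to 11.7%. Applying Clopper-Pearson to the effective sample size moves the upper limit to 12.7%, 13.6%, 14.7% and 15.4% at ρ = 0.25, 0.5, 0.8 and 1. The last value is the fully bilateral case, 3/54 subjects (1.2% to 15.4%). With no events, the upper limit is 3.4% for 108 eyes and 6.6% for 54 subjects.

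**Eye rate against subject rate.** P(at least one eye affected) = 2p − P(both). At p = 5.43% this is 10.6%, 9.3%, 8.0%, 6.5% and 5.4% of subjects at ρ = 0, 0.25, 0.5, 0.8 and 1. In counts, 6 affected eyes can be anything from 3 to 6 of 54 subjects (5.6% to 11.1%).

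**BCVA mean.** The naive standard error is 1/√(1 + ρ) of the correct one: 0.82, 0.75 and 0.71 at ρ = 0.5, 0.8 and 1. Approximate coverage, 2Φ(1.96/√(1 + ρ)) − 1, is 89.0%, 85.6% and 83.4%. Simulation with 54 subjects and a t interval (100,000 runs) gives 89.0%, 85.3% and 83.2%.

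**The case against.** The strongest reply is about weight. The study is single-arm and descriptive, SAP 6.2 disclaims inference on safety, and no success criterion or stopping rule uses these limits. That stands. It does not make an interval labelled 95% correct, and these are the only uncertainty statements planned for ocular events.

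Second, exact coverage is a sawtooth in n and p, so single values can mislead. This is fair. At 68 subjects and ρ = 1, the 81.4% at p = 5.43% becomes 91.6% at p = 5% and 87.0% at 6%. Averaged over true rates of 2% to 10%, coverage at ρ = 0.5 and 0.8 is about 92.8% and 89.7% for 54 subjects, but 94.8% and 92.2% for 27. The pooled shortfall remains; by group at moderate correlation it is small.

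Third, 5.43% need not be the ocular eye rate. At 2% with 54 subjects, coverage is 95.1%, 93.3% and 90.6% at ρ = 0.5, 0.8 and 1, and every miss is on the lower side, so the upper limit does not understate risk. This also stands.

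Fourth, the BCVA interval is attached to the mean at each visit. SAP 6.3.2 specifies no CI for the change from Baseline, which carries more of the safety message.

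Fifth, the table shells are a separate document and might hold a subject count. But SAP 6.3.1 fixes the ocular tables at eye level, so its general wording about subjects or eyes does not supply one. With few events, the count could be made from the TEAE listing, where ocular events are flagged; a reader should not have to do so.

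**Conclusion.** Both parts hold. The planned intervals for ocular TEAEs and mean BCVA rest on an independence assumption that two eyes of one subject are unlikely to meet, and the plan makes no allowance for it. For ocular TEAEs pooled over 54 subjects at a true eye rate of 5.43%, coverage falls to about 88% to 92% for correlations of 0.5 to 1.0; for mean BCVA it falls to about 83% to 89%. By group the size depends on the final n and the true rate, from near nominal to clearly short. These figures rest on an assumed correlation, an assumed eye rate and equal rates in the two eyes. At a correlation of 0.25 the pooled TEAE interval is close to nominal (94.5%).

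The gap in the tables does not depend on any of these assumptions: nothing in SAP 6.3.1 or the section 13 list gives the number of subjects with any TEAE or any ocular TEAE. The consequence is a misstated precision and a missing headline count, not a wrong decision. It should be fixed before the tables are produced.

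**What to change.** - **SAP 6.3.1 and section 13:** add the number and percentage of subjects, with a Clopper-Pearson CI, for any TEAE and for each row of the ocular TEAE summary. A subject counts once if either eye is affected.
- **Eye-level ocular table:** keep the counts and percentages of eyes, and either omit the CI or replace it with one that treats the subject as the cluster.
- **SAP 6.3.2:** base the CI for mean BCVA on each subject's two-eye mean, or on a model with subject as the cluster.

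The cost is some SAP wording and two or three table changes. The eye is already recorded for each ocular event and BCVA is already collected by eye, so no new data are needed. The drawback is wider intervals.

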6.3.2. BCVA

BCVA will be assessed per standard practice at the Screening/Baseline visit (Day 1) and at Visit 3 (and at unscheduled and early exit visits, as necessary).

For each eye, the distance visual acuity (VA) will be collected as per the site's standard of care practice using charts validated for the specific testing distance, which may include for example, 6 m for Snellen chart, 20 ft for Snellen chart, decimal chart and logMAR score. The values for BCVA will be presented in logMAR. BCVA will be summarized as a continuous variable at each analysis visit (Baseline and Visit 3) [eye-level summary]. The mean BCVA score will be presented together with the corresponding 95% CI. In addition, the change from Baseline will be summarized at Visit 3.

A supportive listing for BCVA assessments will be provided.

Derivations:

- BCVA (logMAR) = $-\log_{10} (20 / \text{Snellen VA 20 ft fractions})$ if measured in 20 ft for Snellen chart.
- BCVA (logMAR) = $-\log_{10} (6 / \text{Snellen VA 6 m fractions})$ if measured in 6 m for Snellen chart.
- BCVA (logMAR) = $-\log_{10} (\text{decimal acuity})$ if measured in decimal chart.

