3.6. Pooling of Centers

Summaries will be provided pooled for all sites overall and by group if not indicated otherwise.

4. Subject Characteristics

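### SAP 6.3.2 names the divisor in both Snellen-to-logMAR conversions as the Snellen fraction; the denominator was probably meant, and the label should be corrected because the literal formula gives the wrong sign and offset

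*SAP*

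**What the plan says.** BCVA is one of four safety endpoints (Protocol 6.3.3; SAP 6.1). SAP 6.3.2 lets each site use its own standard chart and gives as examples "6 m for Snellen chart, 20 ft for Snellen chart, decimal chart and logMAR score". It then sets a common scale: "The values for BCVA will be presented in logMAR". The mean and its 95% CI are reported by eye at Baseline and Visit 3, and "the change from Baseline will be summarized at Visit 3".

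Three conversion lines follow (the stray symbols in the first two quotes are formula markup):

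- 20 ft Snellen: the negative log10 of 20 divided by "Snellen VA 20 ft fractions})$ if measured in 20 ft for Snellen chart".
- 6 m Snellen: the negative log10 of 6 divided by "Snellen VA 6 m fractions})$ if measured in 6 m for Snellen chart".
- Decimal: the negative log10 of the decimal acuity, "if measured in decimal chart".

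On pooling, SAP 3.6 states: "Summaries will be provided pooled for all sites overall and by group if not indicated otherwise". Protocol 8.2 says only that suitable conversions to logMAR will be applied and gives no formula. Neither document defines the fraction term as the denominator or shows how the eCRF stores a Snellen result.

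**The concern.** A derivation line exists so that a programmer and an independent checker reach the same number without guessing. Here the only written specification names the wrong quantity. The whole fraction is 20/x or 6/x, and the formula works only if the divisor is x alone. A programmer who follows the words gets a value that falls as acuity worsens on Snellen charts, while decimal and logMAR charts give a value that rises.

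The derived value feeds the BCVA visit means and CIs, the change from Baseline (Table 14.3.2.1) and the baseline characteristics (SAP 4.3). The table list shows no categorical or lines-lost BCVA summary in which a sign error would show up separately.

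**Working it through.** The documents state no BCVA figure to reproduce, so the check evaluates the SAP's own formulas against each other. The reference is the decimal line, logMAR = -log10(f), where f is acuity as a decimal (20/40 = 6/12 = 0.5).

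**Literal reading: the divisor is the fraction f.**

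- 20 ft: -log10(20/f) = -log10(20) + log10(f) = -1.301 - (true logMAR).
- 6 m: -log10(6/f) = -log10(6) + log10(f) = -0.778 - (true logMAR).

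Each Snellen line is a constant minus the true value. The sign is reversed, and the two constants differ by 1.301 - 0.778 = 0.523.

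**Denominator reading: the divisor is x = 20/f or 6/f.**

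- 20 ft: -log10(20/(20/f)) = -log10(f).
- 6 m: -log10(6/(6/f)) = -log10(f).

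Both equal the decimal line.

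| Acuity | 20 ft, literal | 6 m, literal | Decimal line | Both Snellen lines, denominator |
|---|---|---|---|---|
| 20/20 = 6/6 = 1.0 | -1.301 | -0.778 | 0.000 | 0.000 |
| 20/40 = 6/12 = 0.5 | -1.602 | -1.079 | +0.301 | +0.301 |
| 20/200 = 6/60 = 0.1 | -2.301 | -1.778 | +1.000 | +1.000 |

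**Change from Baseline under the literal reading, acuity falling from 1.0 to 0.5.**

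- 20 ft: -1.602 - (-1.301) = -0.301.
- 6 m: -1.079 - (-0.778) = -0.301.
- Decimal: 0.301 - 0.000 = +0.301.

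The offset cancels when an eye is measured on the same chart type at both visits, but the sign error does not. The offset survives in the visit means. It also survives in the change for any eye that switches chart type: 20/20 on a 20 ft chart at Baseline and decimal 1.0 at Visit 3 would show 0.000 - (-1.301) = +1.301 with no true change.

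**Pooled change under the literal reading.** The documents do not give the chart mix. Assume that every eye halves its acuity and that a share s of eyes is measured on Snellen charts, with the rest on decimal or logMAR charts. The pooled mean change is then (1 - s)(0.301) + s(-0.301) = (1 - 2s) x 0.301.

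| s (assumed) | Pooled mean change |
|---|---|
| 0 | +0.301 |
| 0.25 | +0.151 |
| 0.5 | 0.000 |
| 0.75 | -0.151 |
| 1 | -0.301 |

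The true value is +0.301 in every row.

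**The case against.** The best answer is that the harmful reading is the less likely one. Both Snellen lines keep the test distance as numerator and leave one entry to fill, just as acuity is written on a chart. If the entry were already the whole fraction, there would be no need for a leading 20 or 6, nor for two separate Snellen lines. The decimal line is right, so the author knew the conversion. This argument stands on intent. It does not change what is written, because following the words exactly gives the wrong answer.

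A second answer is that the error would be noticed. SAP section 9 requires derived variables to be checked, baseline characteristics are tabulated by site (Table 14.1.3.1.2), and BCVA assessments are listed. Normal eyes at -1.30 or -0.78 should stand out. These are real safeguards, but a check made against the written formula could reproduce the fault.

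A third answer is that BCVA is a descriptive summary with no hypothesis, and no decision rule rests on it. That is correct and limits the severity.

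A reader might infer that the plan reverses a safety endpoint, or that losses and gains will cancel in the pooled change. The documents do not support either. The first requires the literal reading to be programmed and to pass QC. The second also requires a mix of Snellen with other chart types, and the SAP lists chart types only as examples.

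**Conclusion.** The point holds as a wording error in a derivation formula, of low severity. It is not a disputed choice of analysis. As labelled, the two Snellen conversions return a constant (-1.301 or -0.778) minus the true logMAR; with the denominator as divisor they are correct and agree with the decimal line.

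Every consequence is conditional on the literal formula being programmed. In that case visit means for Snellen-measured eyes would be displaced and reversed in direction, and a halving of acuity would appear as -0.301 instead of +0.301. Eyes measured on decimal or logMAR charts would be unaffected. How far the pooled change would be distorted depends on the chart mix, which is an assumption here: anywhere from none at s = 0 to full sign reversal at s = 1. The documents do not show that any output will be wrong.

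**What to change.** In SAP 6.3.2, replace the word fractions with denominator in both Snellen lines, giving -log10(20 / denominator) and -log10(6 / denominator). Equivalently, write both as -log10(Snellen fraction).

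Add a programming check that 20/20, 6/6 and decimal 1.0 all return 0.00, and that 20/40, 6/12 and decimal 0.5 all return +0.301. The second set is what tests the sign.

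The cost is one word in each of two lines and one check. No data collection, design or sample size changes.
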